6.1.2 Sensitivity analyses

The following sensitivity analyses will be performed:

- The primary endpoint analysis will be repeated on the mITT population
- The primary endpoint analysis will be repeated on the PP population.
- The primary endpoint analysis will be repeated on the ITT population with a constrained definition of time to platelet count response. For this analysis, scenarios 2, 5 and 8 will be considered as non response scenarios. The corresponding new censoring time are presented in Table 3 below.

Table 3: Constrained censoring and event plan (for scenarios 2, 5 and 8)

Scenario	Response	Censored	Time to event / censoring time (days)	Graphical representation (grey bar represents dPE)
2) Initial platelet count $\geq 150 \times 10^9/L$ at day x with subsequent stop of dPE within 5 days. Platelet count dropped below $150 \times 10^9/L$ between day x and stop of dPE on day y ($y \leq 45d$) and was not $\geq 150 \times 10^9/L$ by the stop of dPE	No	1	y	
5) Platelet count $\geq 150 \times 10^9/L$ at day x with subject early terminated within 5 days (on day y) while on dPE	No	1	y	
8) Platelet count $\geq 150 \times 10^9/L$ at day x with stop of dPE 5+ days later ($y > 0d$), platelet count stays $\geq 150 \times 10^9/L$ as of day x ($x+y \leq 45d$)	No	1	x+y+5	

- The primary endpoint analysis will be repeated on the ITT population with time to platelet count response defined as the first time platelet count is $\geq 150 \times 10^9/L$ without the requirement to stop daily PE within 5 days. Consequently, only subjects who have no platelet count $\geq 150 \times 10^9/L$ within 45 days of the first i.v loading dose of study drug after randomization, or who were early terminated before reaching platelet count $\geq 150 \times 10^9/L$ are censored for the analysis, with time of censoring at 45 days, or at time of early termination, whichever comes first. Time of stop of daily PE will have no

influence on reaching the endpoint or on censoring time. The scenarios are specified below in Table 4.

Table 4: Censoring and event plan (dPE stop within 5 days not required)

Scenario	Response	Censored	Time to event / censoring time (days)
1) Subject has event within 45 days, on day x.	Yes	0	x
2) Subject has no event within 45 days, and subject has no early termination within 45 days.	No	1	45
3) Subject has no event before early termination on day x, before day 45.	No	1	x

A detailed list of tables, listings and figures can be found in Section [14.2](#), Section [16.2](#) and Section [15.1](#), respectively.

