3.2 Determination of sample size

The primary hypothesis of interest in this study is to test the superiority of caplacizumab compared to placebo with respect to the time to platelet count response (initial platelet count $\geq 150 \times 10^9/L$ with subsequent stop of daily PE within 5 days). The required sample size is

calculated to obtain a power of at least 80% to detect a significant reduction in time to platelet count response using a two-sided Log-rank test, at a significance level of 5%. The accrual period is taken to be 2.5 years and the time-to-event period is set at 45 days. An estimated reduction of time to platelet count response for subjects in the caplacizumab arm of 40% is assumed. With a median time to response in the placebo arm assumed to be 7 days, this would correspond with a median time to response in the caplacizumab arm of 4.2 days. In addition, an expected drop-out rate of 10% in the first 10 days after first administration of study drug is taken into account in the calculations. Based on these assumptions a total sample size of 132 subjects (121 events) will provide a power of 80%.

A total sample size of 132 subjects will also provide approximately 83% power to detect a 20% reduction in the first key secondary endpoint, using a two-sided chi-squared test with a large sample approximation and a 5% significance level. This assumes incidence rates of 30% and 10% in the placebo and caplacizumab arms, respectively.

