6 EFFICACY

6.1 Primary efficacy endpoint evaluation

6.1.1 Primary efficacy analysis

The primary endpoint of the study is: time to platelet count response. Platelet count response is defined as initial platelet count $\geq 150 \times 10^9/L$ with subsequent stop of daily PE within 5 days. It refers to the first time both conditions, platelet count above $150 \times 10^9/L$ and the stop of dPE within 5 days, are met; so it is not necessarily the first time the platelet count goes above $150 \times 10^9/L$.

Only data from the double blind daily PE period up to the cut-off point will be used for the analysis of the primary endpoint. The data cut-off point is defined by either:

- 45 days of daily PE after the start of study drug,
- The stop of daily PE
- The stop of study treatment drug,

[figure not shown]
[figure not shown]
[figure not shown]
whichever occurs first.

[figure not shown]
[figure not shown]
[figure not shown]
[figure not shown]
The time to platelet count response is calculated as the time of the event/censor – time of first i.v. loading dose of study drug after randomization + 1 minute. The time to response will be represented by number of days with two decimal digits.

[figure not shown]
[figure not shown]
[figure not shown]
For the platelet count measurements with missing time part, the missing sample time will be imputed using the first dosing time minus 1 minute for the subject.

Depending on the time of platelet count $\geq 150 \times 10^9/L$, the time of stop of daily PE and the stop of study drug treatment, different potential scenarios for the event time and censoring of observations are possible. These are presented in Table 2.

Table 2: Censoring and event plan

Scenario	Response	Censored	Time to event / censoring time (days)	Graphical representation (grey bar represents dPE)
1) Initial platelet count $\geq 150 \times 10^9/L$ at day x with subsequent stop of dPE within 5 days, platelet count stays $\geq 150 \times 10^9/L$ as of day x ($x \leq 45d$)	Yes	0	x	
2) Initial platelet count $\geq 150 \times 10^9/L$ at day x with subsequent stop of dPE within 5 days. Platelet count dropped below $150 \times 10^9/L$ between day x and stop of dPE on day y ($y \leq 45d$) and was not $\geq 150 \times 10^9/L$ by the stop of dPE	Yes	0	x	
3) No platelet count $\geq 150 \times 10^9/L$ within 45 days of continuous dPE	No	1	45	

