4) No platelet count $\geq 150 \times 10^9/L$ and at day x subject early terminated with no initial platelet count response ($x \leq 45d$)	No	1	x	
5) Platelet count $\geq 150 \times 10^9/L$ (at day x) after being below $150 \times 10^9/L$, with subject early terminated within 5 days while on dPE	Yes	0	x	
6) Stop of dPE at day x without platelet count $\geq 150 \times 10^9/L$ ($x \leq 45d$)	No	1	x	
7) Stop of dPE at day x without platelet count $\geq 150 \times 10^9/L$ and platelet count $\geq 150 \times 10^9/L$ at day x+y ($x \leq 45d$, $y > 0d$)	No	1	x	

8) Platelet count $\geq 150 \times 10^9/L$ at day x with stop of dPE 5+y days later ($y > 0$), platelet count stays $\geq 150 \times 10^9/L$ as of day x ($x+y \leq 45$ days)	Yes	0	x+y	
9) Platelet count $\geq 150 \times 10^9/L$ at day x with stop of dPE 5+y days later ($y > 0$), platelet count has not been $\geq 150 \times 10^9/L$ between day x+y and day x+y+5 ($x+y+5 \leq 45$ days)	No	1	x+y+5	
10) Study drug withdrawn at day x with no Platelet count $\geq 150 \times 10^9/L$, and the subject early terminated y days later ($y > 0$, $x+y \leq 45$ days). The subject was still on dPE until early termination	No	1	x	

Time to platelet count response in the caplacizumab arm and placebo arm will be compared by conducting a two-sided stratified Log-rank test based on a Kaplan-Meier (KM) analysis, with severity of neurological involvement (according to the GCS, stratification factor used in randomization: $\leq 12 / 13-15$) as stratification factor. The resulting p-value will be compared with the significance level α of 5%. In case the p-value is smaller than 0.05 and the estimated median time to platelet count response in the caplacizumab treatment group is smaller than in the placebo treatment group, a significant reduction of time to platelet count response by caplacizumab will be concluded and the primary endpoint will have been met.

This analysis will be performed on the ITT population. Subjects will be analyzed according to the treatment to which they were assigned. Switch of subjects who experience a recurrence of TTP during the study to open-label caplacizumab will not affect the primary efficacy endpoint analysis as a recurrence can only occur after platelet count response, i.e. initial platelet count $\geq 150 \times 10^9/L$ with subsequent stop of daily PE within 5 days, has been reached.

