Table 14.2.1.1.7: EFF: Platelet count – Sensitivity: Time to platelet count response (ITT - Constrained response definition)

Similar to primary endpoint with constrained definition of response by considering efficacy scenario 2, 5 and 8 as non-responders. Kaplan-Meier analysis stratified for GCS at randomization, including a two-sided stratified Log-rank test. The output will include number of events, number of censored values, median, 25% percentile and 75% percentile of time to event with 95% CIs and p-value of the log-rank test as well as the hazard ratio (including CI) of the corresponding Cox proportional hazards model (see table 14.2.1.1.8 below for more details on the Cox model).

The table will be presented both by GCS category, and overall, i.e. unadjusted by GCS category.

Population: ITT population.

Table 14.2.1.1.8: EFF: Platelet count – Sensitivity: Cox proportional hazards model on Time to platelet count response (ITT - Constrained response definition)

Similar to primary endpoint with constrained definition of response by considering efficacy scenario 2, 5 and 8 as non-responders

Cox proportional hazards regression model with time to platelet count response as dependent variable and treatment group and GCS category as independent variables. Table consists of 3 parts:

Part 1: Results of the Cox proportional hazards model including hazard ratio and CI on hazard ratio.

Part 2: Assumption testing including supremum test on proportion of simulated score processes that yielded a maximum score larger than the maximum observed score and a graphical representation of observed score processes per covariate

Part 3 (conditional): Results of the expanded Cox proportional hazards model including hazard ratio and CI on hazard ratio. This part will only be reported when the original assumption of proportional hazards does not hold and time interaction(s) need to be added.

Population: ITT population.

Table 14.2.1.1.9: EFF: Platelet count – Sensitivity: Time to first platelet count $\geq 150 \times 10^9/L$ (ITT - dPE stop within 5 days not required)

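### The constrained sensitivity analysis drops its own non-responders from the risk set on the day plasma exchange stops, so it is a weak stress test of the primary result

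*SAP*

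**What the plan says.** SAP 6.1.1 uses only double-blind daily-PE data up to a cut-off: Day 45, the stop of daily PE or the stop of study drug, whichever is first. Table 2 then codes:

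- Scenario 3, no qualifying count "within 45 days of continuous dPE": non-response, censored at Day 45.
- Scenarios 6 and 7, both opening with "Stop of dPE at day x without platelet count" at the threshold: non-response, censored on day x, the PE-stop day. In Scenario 7 the count reaches 150 later and is still scored as non-response.
- Scenario 9: non-response, censored at x+y+5. PE stops 5+y days after day x, so this too is the PE-stop day.
- Scenario 4, early termination without response: coded exactly like Scenarios 6 and 7.

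SAP 6.1.2 defines the constrained analysis: "For this analysis, scenarios 2, 5 and 8 will be considered as non response scenarios". Table 3 censors Scenario 2 at day y and Scenario 8 at x+y+5, again the PE-stop day in both. The description of Table 14.2.1.1.7 repeats the intent: "by considering efficacy scenario 2, 5 and 8 as non-responders". A further sensitivity analysis (Table 4) ignores PE stop and censors subjects without a count of 150 at Day 45 or early termination. Protocol 3.6.4.1 says that an endpoint not reached within 45 days is censored and leaves the details to the SAP.

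**The concern.** Once PE has stopped without a qualifying response, the SAP's own rule means that the subject cannot become a responder. Scenario 7 makes that explicit. Scenario 3 has the same outcome and counts against its arm until Day 45. Subjects in Scenarios 6, 7 and 9, and those moved to non-response in Table 3, leave the risk set at PE stop and are indistinguishable from a dropout.

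The constrained analysis is the one planned run that tightens the definition of response. If the subjects it reclassifies then disappear from the denominator, it can look reassuring without having tested much. A reader would also not learn how the log-rank result and hazard ratio behave when such failures are kept as failures.

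**Working it through.** **1. Codings side by side**

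| Scenario | Table 2 (primary) | Table 3 (constrained) | Table 4 (PE stop ignored) |
|---|---|---|---|
| 2 | response at x | non-response, censored at PE stop (y) | response at x |
| 3 | censored at Day 45 | unchanged | censored at Day 45 |
| 6 | censored at PE stop (x) | unchanged | censored at Day 45 or early termination |
| 7 | censored at PE stop (x) | unchanged | response if the count reaches 150 by Day 45 |
| 8 | response at x+y | non-response, censored at PE stop (x+y+5) | response at x |
| 9 | censored at PE stop (x+y+5) | unchanged | response at x |

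The mITT and per-protocol repeats use the Table 2 rule. So Scenario 6 is held to Day 45 in one planned run. Scenarios 2, 8 and 9, and Scenario 7 with recovery by Day 45, are never held there as failures. As a side point, Table 3 limits Scenario 8 to x+y of at most 45 but censors at x+y+5, which can reach Day 50.

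**2. Reproducing the design**

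Inputs (SAP 3.2): "using a two-sided Log-rank test, at a significance level of 5"%; placebo median 7 days; caplacizumab median 4.2 days; 10% dropout in 10 days; 45-day horizon.

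- Ratio 4.2/7 = 0.60, so ln 0.60 = -0.511.
- Schoenfeld events: 4(1.960 + 0.842)²/0.511² = 120.3, rounded up to 121.
- Power with 121 events: Φ(√121/2 × 0.511 - 1.960) = 80.2%.
- Exponential times with dropout rate -ln(0.9)/10 per day: event probability 0.897 (placebo) and 0.940 (caplacizumab), mean 0.9185. Then 121/0.9185 = 131.7, so N = 132.

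This matches the SAP: "a total sample size of 132 subjects (121 events) will provide a power of 80"%.

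**3. Failures under the primary definition**

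Simulated log-rank test, 66 per arm, exponential response with medians 7 and 4.2 days. Failures are censored either at PE stop or at Day 45. A hazard ratio above 1 means faster response on caplacizumab. The number of failures is an assumption.

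| Failures | HR, PE stop | HR, Day 45 |
|---|---|---|
| none | identical | identical |
| 1 per arm | 1.69 | 1.58 |
| about 3% per arm (2/66) | 1.68 | 1.53 |
| about 1 placebo, 3 caplacizumab | 1.67 | 1.39 |
| about 3 placebo, 1 caplacizumab | 1.71 | 1.72 |

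Other assumptions on when PE stops give 1.65 to 1.69 falling to 1.34 to 1.39 in the fourth row.

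Larger shares, as the chance of a significant result for caplacizumab (PE stop versus Day 45):

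- 5% in both arms: 78% versus 52%.
- 10% in both arms: 75% versus 37%.
- 10% on caplacizumab only: 57% versus 5%.
- 10% on placebo only: 90% versus 98%.

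**4. The constrained analysis**

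If 10% of responders in each arm were reclassified as Scenario 2 or 8, the HR is 1.61 to 1.64 under Table 3 as written and 1.35 to 1.38 if all are held to Day 45. Power is 68% to 70% versus 36% to 39%. This pools both scenarios, so it is an upper illustration.

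**5. Error rate and the Kaplan-Meier curve**

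With equal timing and equal failure shares, both rules reject in about 5% of null trials. What changes is the quantity estimated. With a failure share of 10% and no dropout, one minus Kaplan-Meier at Day 45 under PE-stop censoring is 1 - exp(-0.9 × 45 × ln2/7) = 98.2% on placebo. The true proportion responding is 0.9 × (1 - exp(-45 × ln2/7)) = 89.0%. For caplacizumab the figures are 99.9% and 89.9%.

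**The case against.** Most of the case on the other side stands, and it limits the point.

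- PE stop is a pre-specified cut-off and acts as a competing event. Censoring there compares response rates among subjects still on PE. That is valid for the log-rank test and hazard ratio without supposing what stopped subjects would have done later; the supposition matters only when one minus Kaplan-Meier is read as the proportion responding. A reader might infer that the primary test is wrong or its error rate inflated. The documents and the null simulation do not support that.
- A reader might call all these subjects definitive failures. Scenario 8 is not: its count stays at or above 150, the primary analysis scores it as a response, and the protocol sets a minimum but no maximum for PE after normalization. Holding it to Day 45 is a deliberately severe choice.
- A reader might infer that no planned run tests any of this. Table 4 already does so for Scenario 6 and leaves Scenarios 1, 2, 3 and 5 coded as in Table 2.
- Day-45 handling should not be selective. Scenario 10 also ends at a cut-off after which no response counts, and early termination in Scenario 4 can include death.
- SAP 6.2.1 describes stopping PE before a count of 150 as exceptional, so the numbers may be small. Event and censoring counts are tabulated, and platelet data are listed by subject.

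What remains is that no planned run keeps Scenarios 2, 8 and 9, or Scenario 7 with recovery by Day 45, as failures, and Table 3 does not fully penalise the subjects it reclassifies.

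**Conclusion.** The point holds as a weakness of the sensitivity plan. The primary analysis can stand as written. The constrained analysis labels subjects as non-responders and then lets them leave like dropouts, so it tests the stricter definition only in part.

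The size is unknown, because the share of subjects in these scenarios is not in the documents. It is nil with no failures. A few failures, equal across arms or mainly on caplacizumab, can lower the hazard ratio noticeably (1.68 to 1.53, or 1.67 to 1.39). A few mainly on placebo leave it almost unchanged, and failures confined to placebo would strengthen it. The direction is therefore not fixed in advance. All these figures rest on exponential response times, the SAP's design medians and assumed failure counts; they are illustrations and not forecasts.

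**What to change.** 1. In Table 3, censor Scenario 2 at Day 45, as Scenario 3 is. Show Scenario 8 both ways, at PE stop (no later than Day 45) and at Day 45, because its count stays at or above 150.
2. Add one sensitivity analysis with the primary response definition unchanged, in which Scenarios 6, 7 and 9 stay at risk to Day 45. State in advance how that run treats Scenario 10 and deaths within Scenario 4.
3. Report the number of subjects in each scenario by arm, beside the primary log-rank test and hazard ratio.

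The cost is a changed censoring time for Scenario 2, a second version for Scenario 8, one extra run and one small table. No new data are needed. The downside is that the sensitivity hazard ratio may be less favourable than the one now planned. If such subjects prove rare, the same output shows that the result does not depend on the choice.

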6.2 Secondary Efficacy Endpoints Evaluation

6.2.1 Key secondary endpoints

Key secondary endpoints are defined in Section [3.3.2.1](#).

Confirmatory hypothesis testing will be conducted only for the key secondary endpoints. In order to control the rate of false positive conclusions with a family-wise error rate of 5%, a fixed sequence approach will be applied. The key secondary endpoints are hierarchically ordered. This allows statistical testing for these endpoints at the same nominal significance level of 5% without adjustment, as long as the tests occur in the pre-defined sequential order, and given that all null hypotheses to be tested for endpoints with a higher rank (including the primary endpoint) are rejected. As soon as a test is not statistically significant for a certain endpoint, i.e. as soon as the sequence breaks, no confirmatory testing will be done for remaining endpoints lower in the ranking. Statistical comparison between the two treatment arms for the key secondary endpoints will be done by means of the following planned analyses (in hierarchical order):

1. Proportion of subjects with TTP-related death, a recurrence of TTP, or at least one treatment-emergent major thromboembolic event (e.g., myocardial infarction, cerebrovascular accident, pulmonary embolism or deep venous thrombosis [DVT]) during the overall treatment period (including extensions). Start and end times of the overall treatment period are defined in Section [4.4.1](#). A Cochran-Mantel-Haenszel (CMH) test will be conducted with adjustment for GCS category (stratification factor used in randomization). For both treatment groups, only events that have occurred prior to a switch to open-label caplacizumab will be evaluated for this analysis.

This composite endpoint consists of the following components:

- TTP-related death: adverse event categorized as 'clinically significant TTP event' and documented as 'death due to TTP' and/or adverse events with outcome 'fatal', adjudicated as TTP related (see below).
- TTP recurrence: recurrent thrombocytopenia after initial recovery of platelet count, requiring re-initiation of daily PE. Depending on the timing of recurrence, it is defined as:
 - Exacerbation: recurrence occurring during the first 30-days post-daily PE period
 - Relapse: recurrence occurring after the 30-days post-daily PE period; only relapses within the overall treatment period are taken into account for the key secondary endpoint.

Exacerbations and relapses will be documented as serious adverse events. Note that, exceptionally, daily PE may have been stopped before an initial platelet count $\geq 150 \times 10^9/L$ is reached, by investigator's decision. It is recognized that in this case the subject can still experience an exacerbation or relapse requiring re-initiation of daily PE if documented as described above.

- Treatment-emergent major thromboembolic event: e.g., myocardial infarction, cerebrovascular accident, pulmonary embolism or DVT, confirmed after adjudication (see below).

If a potential major thromboembolic event or TTP-related death occurs, the investigator will be requested to provide additional information for adjudication by a blinded independent committee. Only events that are confirmed after adjudication will be used for the analysis. More details are provided in CSP Section 3.4.3.6 and [Appendix B: Adjudication charter](#).

2. Proportion of subjects with a recurrence of TTP in the overall study period (including the FU period). A CMH test will be conducted with adjustment for GCS category (stratification factor used in randomization). For both treatment groups, only recurrences that have occurred prior to a potential switch to open-label caplacizumab will be evaluated for this analysis.
3. Proportion of subjects with refractory TTP, defined as absence of platelet count doubling after 4 days of standard treatment, and LDH $>$ ULN. A CMH test will be conducted with adjustment for GCS category (stratification factor used in randomization). Refractory TTP is derived as follows: (platelet count after 4 days of standard treatment / platelet count at start of standard treatment) $<$ 2 and LDH $>$ ULN after 4 days of standard treatment. Platelet count and LDH at Day 5 will be used for this analysis. Subjects who have reached platelet count response (primary endpoint) by Day 5 will not be considered as having a refractory TTP.

Subjects discontinued (lost to follow-up, withdrew consent, etc...) before day 5 will be excluded from the analysis.

CONFIDENTIAL

Missing values will be imputed using multiple imputation (Markov Chain Monte Carlo) by averaged simulated parameter values. The number of simulation iterations will be adapted to the proportion of missing values (0-10% missing values: 20 iterations, 10-20% missing values: 100 iterations) to keep the relative efficiency (RE) of multiple imputation under control (Rubin, 1987).

The following sas code will be used as starting point for the multiple imputation:

```
proc mi data=original n impute=number seed=1 out=imputed minimum=0
round=1;
  by studyid trt01pn trt01p;
  mcmc impute=full;
  var _day1 _day2 _day3 _day4 _day5;
run;

where
ORIGINAL is the input dataset
IMPUTED is the data after imputation
NUMBER is the number of imputation depending on the percentage of
missingness
STUDYID is the study identifier
TRT01P and TRT01PN are respectively the categorical and numeric
versions of the planned treatment groups used for the subjects during
the DB treatment period
_DAYx (x=1 to 5) are the measurements for each subjects from day 1 to
day 5
```

4. Time to first normalization of all three organ damage marker levels, i.e. LDH, cTnI and serum creatinine. Time to first normalization of LDH, cTnI and serum creatinine is defined as: first time of LDH \leq ULN and cTnI \leq ULN and serum creatinine \leq ULN - time of first i.v. loading dose of study drug after randomization + 1 minute. The time to normalization will be represented by number of days with two decimal digits. Subjects in either initial treatment group who have switched to open-label caplacizumab before having reached the endpoint will be censored at time of switch. All on-treatment records during DB treatment period will be used. A stratified Log-rank test will be conducted based on a KM analysis with adjustment for GCS category and for an additional factor defining whether the subject has abnormal values at baseline for LDH only (not for cTnI or for serum creatinine) or not.

In addition to the confirmatory statistical tests, standard summary statistics will be provided for all key secondary endpoints. For the first key secondary endpoint 'proportion of subjects with TTP-related death, a recurrence of TTP, or at least one treatment-emergent major thromboembolic event during the overall treatment period (including extensions)' and for the second key secondary endpoint 'proportion of subjects with a recurrence of TTP in the overall study period' separate summary statistics will be included for the OL Caplacizumab treatment group. For these endpoints also the number of events will be reported.

All analyses will be run on the ITT population.

A detailed list of tables, listings and figures can be found in Section [14.2](#), Section [16.2](#) and Section [15.1](#), respectively.

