- Proportion of subjects who have a platelet count $\geq 150 \times 10^9/L$ on Day 1, 2, 3, 4, 5 and Day 10 and end of study drug treatment (i.e., last weekly visit during the DB or OL treatment period) will be summarized by treatment group (Caplacizumab, Placebo, OL Caplacizumab).
- Proportion of subjects with refractory TTP, defined according to Scully et al. (2016) as lack of sustained platelet count increment or platelet counts $< 50 \times 10^9/L$ and persistently raised LDH ($> 1.5 \times$ ULN) despite 5 plasma exchanges and steroid treatment will be summarized by treatment group (Caplacizumab, Placebo). Refractory TTP is derived as follows: (platelet count at Day x $<$ platelet count at Day x-1 for at least 1 value of x with x=2,...,5) and (LDH $> 1.5 \times$ ULN from Day 1 to Day 5). Subjects who have reached platelet count response (primary endpoint) by Day 5 will be considered as not refractory to TTP. Missing values will be imputed by using multiple imputation (Markov Chain Monte Carlo) by

averaged simulated parameter values, except if the subject discontinued prior to Day 5. In that case, the subject will not be considered in the analysis.

- Time to stop of daily PE: A KM analysis will be conducted with time to stop of daily PE within the DB treatment period as dependent variable and treatment group (Caplacizumab, Placebo) as independent variable. Time to stop of daily PE is defined as: date of daily PE stop - date of first i.v. loading dose of study drug after randomization + 1 day.
- The number of PE days and the total PE volume (absolute and normalized) in the DB treatment daily PE period and the overall treatment period will be summarized by treatment group. For this analysis the treatment groups are defined as
 - Caplacizumab + OL Caplacizumab
 - Placebo + OL Caplacizumab

Subjects will thus be analyzed according to their initial treatment group, both before and after switch to open-label caplacizumab. The number of PE days is defined as the total number of days on which PE is documented. The absolute total PE volume is given by the sum over all PE days of the amount exchanged in liter, while the normalized total PE volume is calculated as the sum over all PE days of the multiple of plasma volume exchanged.

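### Key secondary 3: for a subject whose Day 5 count is normal but not doubled, refractory status depends on when daily PE stops after Day 5

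*SAP*

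**What the plan says.** Protocol 3.6.4 defines refractory TTP by two conditions, no doubling of the platelet count after 4 days of standard treatment and LDH above ULN. It gives no exemption.

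SAP 6.2.1(3) makes this operational. The count condition is "platelet count after 4 days of standard treatment / platelet count at start of standard treatment) $<$ 2", the LDH condition is "LDH $>$ ULN after 4 days of standard treatment", and "Platelet count and LDH at Day 5 will be used for this analysis". It then adds the exemption: "Subjects who have reached platelet count response (primary endpoint) by Day 5 will not be considered as having a refractory TTP".

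SAP 6.1.1 requires two things for platelet count response: a count of at least 150 × 10^9/L, and daily PE stopping within 5 days of it. The SAP notes that the response date follows from both, "so it is not necessarily the first time the platelet count goes above" 150. In Table 2, Scenario 8 covers a count that becomes normal at day x "with stop of dPE 5+y days later"; the response is then dated x+y, not x.

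Protocol 3.3.6 sets a 2-day minimum for daily PE after the count reaches 150 and states no maximum.

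SAP 6.2.2 has a second, descriptive refractory endpoint based on a published consensus definition, with an equivalent exemption: "Subjects who have reached platelet count response (primary endpoint) by Day 5 will be considered as not refractory to TTP".

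**The concern.** The endpoint is meant to be read at Day 5, but the exemption imports a condition that may not be known until Day 10 or later. Two subjects with the same counts and LDH on Days 1 to 5 can fall in different classes because PE was stopped one day apart the following week. One of them is then reported as refractory with a normal platelet count.

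Key secondary 3 is confirmatory. If the primary and the first two key secondaries succeed, it decides whether key secondary 4 can be tested (SAP 6.2.1, fixed sequence). A class that turns on later PE decisions also mixes a treatment choice into an endpoint intended to describe early response.

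**Working it through.** The plan gives no rate, power or sample size for key secondary 3, so there is no figure of its own to reproduce. The check applies the rule as written.

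**Inputs**
- Refractory if Day 5 count / start count < 2, and LDH > ULN, and no primary-endpoint response by Day 5 (SAP 6.2.1(3)).
- Response is dated on the first day with a count ≥150 and daily PE stopping within 5 days of that day (SAP 6.1.1, Table 2).
- Entry excludes counts ≥100 (Protocol 3.2.2, criterion 1).
- 132 subjects, 66 per arm (SAP 3.1).

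**When the exemption is lost.** With a count ≥150 on Day 5, response is dated Day 5 or earlier if PE stops by Day 5 + 5 = Day 10. If the count is first normal on Day 5 and PE stops on Day 11, Scenario 8 has x = 5 and 5+y = 6, so y = 1 and the response is dated Day 6.

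**Which counts are exposed.** Let s be the start count and c the Day 5 count. A normal but undoubled count needs 150 ≤ c < 2s, so s > 75. With s < 100, whole-number start counts run from 76 to 99. Day 5 counts run from 150 to 197, because at s = 99 a count of 198 has doubled.

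**Cases** (count first normal on Day 5 and staying normal)

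| Start | Day 5 | Ratio | LDH (× ULN) | PE stop | Response dated | Class |
|---|---|---|---|---|---|---|
| 20 | 160 | 8.0 | 1.2 | Day 14 | Day 9 | not refractory |
| 75 | 150 | 2.0 | 1.2 | Day 14 | Day 9 | not refractory |
| 76 | 151 | 1.99 | 1.2 | Day 14 | Day 9 | refractory |
| 85 | 160 | 1.88 | 1.2 | Day 10 | Day 5 | not refractory (exempt) |
| 85 | 160 | 1.88 | 1.2 | Day 11 | Day 6 | **refractory** |
| 85 | 160 | 1.88 | 0.9 | Day 11 | Day 6 | not refractory |
| 99 | 197 | 1.99 | 1.2 | Day 12 | Day 7 | refractory |
| 99 | 198 | 2.0 | 1.2 | Day 12 | Day 7 | not refractory |

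**Denominator.** The SAP text divides by the count at the start of standard treatment, but its imputation code uses Day 1 to Day 5. The Day 1 count follows the pre-randomization PE, while eligibility may rest on an earlier standard-of-care sample (Protocol 3.4.1.1). If Day 1 is the denominator, s can exceed 99 and the window widens. For example, s = 110 would expose Day 5 counts of 150 to 219 (2 × 110 = 220).

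**How many.** The documents give no start-count distribution. Assume start counts are lognormal, truncated at 100, with median 15–40 and log-SD 0.6–1.0. The share above 75 is then 0.3% to 10.4%, or about 0.4 to 14 of 132. That is a ceiling for entry-limited start counts, before also requiring c between 150 and 2s, LDH > ULN and PE beyond Day 10. Each reclassified subject moves an arm's rate by 1/66 = 1.5 percentage points.

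**Sensitivity of the test, illustrative only.** For a single-stratum CMH test with 66 per arm, a and b events and m = a + b, the statistic is ((a − b)/2)² / [m(132 − m)/(4 × 131)]. The event counts are invented:
- 4 vs 0: 4/0.977 = 4.09, p = 0.043
- 4 vs 1: 2.25/1.212 = 1.86, p = 0.17
- 5 vs 0: 6.25/1.212 = 5.16, p = 0.023
- 8 vs 2: 9/2.328 = 3.87, p = 0.049
- 8 vs 3: 6.25/2.540 = 2.46, p = 0.12

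**SAP 6.2.2.** Here one day-to-day fall in count between Days 1 and 5, plus LDH > 1.5 × ULN from Day 1 to Day 5, is enough. Counts of 20, 90, 160, 155, 170 with such LDH values and PE stopping on Day 11 are classed as refractory because of the step from 160 to 155. No start count above 75 is needed.

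**The case against.** The strongest reply is that the protocol definition has no exemption. A subject going from 85 to 160 with LDH above ULN is refractory by Protocol 3.6.4 whenever PE stops. The SAP exemption already narrows that definition, and a count-only exemption narrows it further. The SAP gives no reason for its exemption, and the trial's own notion of initial recovery (Protocol 3.1.1, definition of exacerbation) also pairs a count of at least 150 with PE stopping within 5 days. This stands, and it is why the change must be recorded as a refinement. It does not remove the inconsistency, because the SAP as written follows neither the plain protocol definition nor a Day 5 rule.

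A second reply is that a single Day 5 count of at least 150 is weak evidence of recovery. In Scenario 9 the count is not at or above 150 in the window before the late PE stop, and Table 2 calls that non-response. This stands as a cost of the fix.

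A reader might infer that continued PE alone turns a subject with a normal count into a refractory one. The documents do not support that: the ratio and LDH conditions must also hold, and any subject starting at 75 or below who reaches 150 has already doubled. A reader might also infer a bias toward one arm. None is shown: Protocol 3.1.3 keeps sites blinded to assignment, and in the p-value examples the extra event can strengthen the result as easily as weaken it.

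**Conclusion.** The point holds as a narrow flaw in the definition. For subjects who start above 75, reach 150 but not twice the start count by Day 5, and still have LDH above ULN, the class is settled by whether PE stops by Day 10.

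The impact on key secondary 3 is low. The number of subjects is probably very small, but the documents give neither a start-count distribution nor a refractory rate, so it cannot be fixed more closely than the assumed ceiling. The 76–99 and 150–197 bounds rest on the entry limit applying to the denominator. The p-values show only that a test with few events can turn on one subject; they do not predict a changed result. The 6.2.2 endpoint is more exposed but carries no hypothesis test, so it adds no confirmatory risk. Severity: minor.

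**What to change.** Before unblinding, replace the exemption in SAP 6.2.1(3) and 6.2.2 by: *Subjects with a platelet count ≥150 × 10^9/L at Day 5, or who have reached platelet count response by Day 5, are not refractory, irrespective of the later date of stop of daily PE.* Record this in SAP 12.1 as a refinement of the protocol definition. In the same edit, state which count is the denominator of the ratio in 6.2.1(3).

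With this wording the 85 to 160 subject is not refractory whether PE stops on Day 10 or Day 11, and no subject with a normal Day 5 count is classed as refractory. In key secondary 3, subjects starting at 75 or below keep their class.

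The cost is one sentence in two sections, one programming condition and one entry in 12.1. The downside is a small further step away from the protocol definition, and exemption of a subject whose single normal Day 5 count later falls. The change concerns classification only and alters no treatment rule.
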